## ABBREVIATIONS AND ACRONYMS

AA-ORS: amino acid–based oral rehydration solution

AE: adverse event

CGH: Kakamega County General Hospital

CRF: case report form

CWC: child welfare clinic

DFID: Department for International Development

DO: direct observation

DSMB: Data and Safety Monitoring Board

EC: ethics committee

EED: environmental enteric dysfunction

ELISA: enzyme-linked immunosorbent assays

EPI: Expanded Program on Immunization

GCP: good clinical practices

GRAS: generally regarded as safe

HCP: health care provider

ICH: International Council on Harmonisation

IDI: in-depth interview

IRB: institutional review board

ISM: independent study monitor

LAZ: Length-for-age z-score

LRS: low-resource settings

MAL-ED: Etiology, Risk Factors and Interactions of Enteric Infections and Malnutrition and the Consequences for Child Health and Development

MOH: Ministry of Health

MUERC: Maseno University Ethics Review Committee

MUAC: mid-upper arm circumference

ORS: oral rehydration solution

PI: principal investigator

Safety, Acceptability, and Feasibility of enterade® Protocol  
V1.7 28 August 2018

PID: Patient Identification Number

PPB: Pharmacy and Poisons Board

RA: research assistant

REC: research ethics committee

SAE: serious adverse event

SOP: standard operating procedure

SUSAR: suspected unexpected serious adverse reaction

Vit. A: vitamin A

WHO: World Health Organization

## STUDY OVERVIEW

Title:	Safety, Acceptability, and Feasibility of enterade® in children at risk for environmental enteric dysfunction in Kakamega County, Kenya
Sponsor:	Drug Development, PATH
Investigators:	USA: [name] (co-PI), [name], [name] Kenya: [name] (co-PI), [name], [name]
Ethics committees:	Maseno University Ethics and Research Committee (MUERC) PATH Research and Ethics Committee (REC)
Regulatory authority:	Kenyan Ministry of Health (MOH) Pharmacy and Poisons Board (PPB)
Phase:	I
Study goals:	Determine the safety, acceptability, and pediatric dosing of enterade® solution, an amino acid–based oral rehydration solution (AA-ORS), for potential use in the management of environmental enteric dysfunction (EED) among children aged 12–24 months in Kenya.
Study objectives:	
 
1. Primary: To determine the safety of a 2-week course of AA-ORS among children with length-for-age Z-scores (LAZ) between –1 and –3.
 
2. Primary: To determine the feasibility and best tolerated dose of AA-ORS among children with LAZ between –3 and –1.
 
3. Secondary: To determine the perceptions among caregivers on the acceptability of AA-ORS as a potential intervention for EED.
 
4. Exploratory: To determine the impact of AA-ORS on markers of metabolism, gut dysfunction, systemic inflammation, and micronutrient status among children with LAZ between –3 and –1.
 

Study endpoints:	
 
1. Primary: Adverse events and serious adverse events through 21 days of follow-up, and changes to dietary and digestive habits through day 14 of follow-up.
 
2. Primary: Average daily product volume consumed through 14 days of follow-up, time trends in average daily volume consumed, and factors that influence children’s willingness and ability to ingest the product as intended.
 
3. Secondary: Key factors that influence caregivers’ willingness to have the product used by their children, and their perception of their children’s response to its consumption.
 
4. Exploratory: Average plasma/serum concentrations of metabolic, gut dysfunction, systemic inflammation, and micronutrient biomarkers at baseline and day 15 of follow-up.
 

Study design:	This is a mixed-methods pilot study to assess the safety, acceptability, and feasible dosage of AA-ORS among children with mild to moderate stunting (LAZ between –1 and –3) who are at risk for EED and to assess the acceptability of this fluid supplementation for their caregivers. During the main study, child participants will be

randomized to receive 14 days of AA-ORS or placebo solution daily, dosing of up to 237 ml over a 3-hour period. Study staff and participants will be blinded to the study product allocation. Caregivers will store and return unused study product. Data collection methods to include direct observation of product consumption, adverse event assessments, structured surveys with caregivers, average daily volume consumed, and measurement of plasma/serum markers of metabolism, gut dysfunction, systemic inflammation, and micronutrient status pre- and post-administration of product.

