#### *Blood Specimen Collection and Processing*

Between 1 and 1.5 ml venous blood will be collected from each child twice—at enrollment and at the post-dosing visit, 15 days after onset of the intervention. A trained phlebotomist will perform venipuncture using a technique appropriate for children who are younger than 2 years old, and a small drop of blood will be blotted from the insertion site and dried on filter paper. Blood samples will be centrifuged into plasma and/or serum within 30 minutes of collection and stored in cryo tubes at less than  $-20^{\circ}\text{C}$  until they can be analyzed. Commercial enzyme-linked immunosorbent assays (ELISA) and a Quansys Biosciences Q-Plex™ panel will be used to quantify plasma/serum micronutrients, EED markers (intestinal fatty acid-binding protein [I-FABP], soluble CD14 [sCD14], glucagon-like peptide 2 [GLP-2], insulin-like growth factor 1 [IGF-1], and fibroblast growth factor 21 [FGF21]), and systemic inflammation (alpha-1-acid glycoprotein [AGP] and C-reactive protein [CRP]). Mass-spectroscopy will be used to evaluate metabolic markers from dried bloodspot (e.g., acylcarnitine profile) to ascertain whether there is a tendency for child metabolism to switch to an oxidative state when supplementing a subset of essential amino acids. Detail provided in Table 5, below.

**Table 5.** Plasma/serum biomarkers assessed in SAFE at enrollment and post-dosing visit.

Biomarker	Assay name	Company	μl of plasma required (per well)
I-FABP	Human I-FABP ELISA	Hycult	25
GLP-2	GLP-2 ELISA Kit	ALPCO	25
IGF-1	Human IGF-I Quantikine ELISA Kit	R&D Systems	20
sCD14	Human CD14 Quantikine ELISA Kit	R&D Systems	10
FGF21	Human FGF-21 Quantikine ELISA Kit	R&D Systems	50
AGP	Q-Plex™ Human Micronutrient (7-Plex)	Quansys	10
CRP			
Ferritin			
sTfR			
RBP4			
Thyroglobulin			
HRP2			
Acylcarnitine	Acylcarnitine profile analysis	Mass spectrometry	40 (80 μl whole blood)
Total			320

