Following the visit, those who are still interested and eligible will be scheduled to undergo the informed consent process and enrollment visit at CGH at a time convenient to them, 1–3 weeks after the immunization or Vit. A supplementation visit, or whenever is convenient for those who had been identified from the CWC register (but did not receive immunizations or Vit. A supplementation). The delayed enrollment visit is to avoid conflating potential immunization-related AEs with those related to the study product. Caregivers will receive a reminder call from study staff the day before their scheduled enrollment visit. During the appointment reminder call, caregivers will be advised of changes that would make them ineligible (to avoid an extra trip to the hospital). These changes include diarrhea in household in past week, child acute illness, and child antibiotic treatment within the past 2 weeks. If the child is no longer eligible based on one of these changes, the enrollment visit will be postponed and rescheduled or cancelled, depending on the caregiver's preference. The caregiver will be told that they have the option to decline to participate at the time they are contacted by the study team or any time thereafter.

Children and their caregivers will be recruited as a dual enrollment participant pair. Upon their return to the facility, the RA will escort the caregiver and child to a private exam room where they will review the consent form and answer questions they may have. The RA will confirm that both the child and caregiver still meet both sets of eligibility criteria. The RA will then obtain written informed consent from willing and eligible caregivers prior to the child medical examination, blood draw, IDI, and administration of AA-ORS or placebo solution.

All participants will be informed that the study does not offer any direct benefit to them and the use of this product is currently for exploratory research purposes only. The study does not aim to assess the reliability or compare the outcomes of AA-ORS to the standard of care. The information participants will provide throughout this study is not considered sensitive and will not pose any significant risk to them personally. Participants have the option to decline being interviewed for the study without any negative consequences.

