#### vii. Exclusion criteria for each group

##### *Exclusion Criteria*

##### Pediatric and caregiver pairs (must meet none of the exclusion criteria for either category):

###### Child:

1. Has any sign of acute illness, including but not limited to fever, cough, and diarrhea.
2. Is wasted (weight for length z-score  $< -2$  or mid-upper arm circumference [MUAC]  $< 12.4$  cm) or has pitting edema.
3. Is exclusively breastfed.

4. Is seeking medical attention at the health facility other than for routine, preventative care (e.g., immunization visit, vitamin supplementation).
5. Has suffered within the prior week from illnesses that might impact nutritional status (e.g., severe diarrhea or pneumonia; vomiting; persistent diarrhea; cleft lip or palate; blindness; tuberculosis; jaundice; renal or cardiac disease; cerebral palsy; known metabolic disorders; and chromosomal disorders, including trisomy 21).
6. Medical history of chronic health condition (i.e., HIV, hepatitis B or C, end stage renal disease, severe liver disease—absence of a diagnosis is sufficient).
7. Participating in any other clinical trials.
8. Recent (prior 2 weeks) use of antibiotics or any other medical treatments (including ORT, but not including vaccines or vitamin/mineral supplementation).
9. Cannot give the necessary biological (blood) sample.

Caregiver:

Reports diarrhea in the household in the prior 7 days.

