**STUDY ENDPOINTS TO BE ANALYZED AND ANALYTICAL METHODOLOGY**

**Primary:** AEs and SAEs through 21 days of follow-up, and changes to dietary and digestive habits through day 14 of follow-up.

*For AEs and SAEs that occur within 21 days of enrollment, statistical comparisons will be made between the AA-ORS and the placebo solution groups using Fisher's exact test. Changes to feeding habits (normal, less frequent/less volume, more frequent/more volume), diarrhea (1–2, 3–4, 5–7, or 7+ events in 24 hours), and vomiting (none, 1, 2–5, > 6 events in 24 hours, or hospitalization) will be made using chi-square tests.*

**Primary:** Average daily product volume consumed through 14 days of follow-up, time trends in daily volume consumed, and factors that influence children's willingness and ability to ingest the product as intended.

*The average daily volume (and statistical distribution) of solution consumed by children over the 2-week period will be calculated. These descriptive data will be pooled from AA-ORS and placebo arms as the solutions are designed to taste the same. Lowess curves will be used to describe trends in volumes consumed, and linear mixed effects models will be used to test for an association between day of follow-up and product volume consumed. We will use linear regression to identify factors (e.g., child weight, length, and age) associated with a child's average daily intake.*

**Secondary:** Key factors that influence caregivers' willingness to have the product used by their children, and their perception of their children's response to its consumption.

*These qualitative analyses will use ATLAS.ti software to identify and group key themes and topics from IDI notes.*

**Exploratory:** Average plasma/serum concentrations of metabolic, gut dysfunction, systemic inflammation, and micronutrient biomarkers at baseline and day 15 of follow-up.

*Metabolic, EED, systemic inflammation, and micronutrient marker data collected at baseline will be pooled across intervention groups and used to generate descriptive statistics for the study population. The same descriptive statistics will be generated for day 15 of follow-up. Paired student's t test will be used to compare these continuous parameters between baseline and day 15 of follow-up.*

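### Ferritin and RBP4 are to be compared as raw averages although CRP and AGP come from the same panel, so a shift in inflammation could be read as a shift in micronutrient status, above all in the baseline to day 15 test.

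*Combined protocol and SAP*

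**What the plan says.** The fourth objective in the Study Overview is "To determine the impact of AA-ORS on markers of metabolism, gut dysfunction, systemic inflammation, and micronutrient status among children". Section C.ii repeats it in more direct terms, as an effect on micronutrient status itself. The endpoint in Section C.xi is "Average plasma/serum concentrations of metabolic, gut dysfunction, systemic inflammation, and micronutrient biomarkers at baseline and day 15 of follow-up".

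Table 5 (Section C.iii, Blood Specimen Collection and Processing) lists AGP, CRP, ferritin, sTfR, RBP4, thyroglobulin and HRP2 under one 7-plex assay. The text above the table classes AGP and CRP as systemic inflammation markers.

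Section C.xi plans three things for these data:

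- Descriptive statistics: "micronutrient marker data collected at baseline will be pooled across intervention groups and used to generate descriptive statistics for the study population", and the same at day 15.
- Within children: a paired Student's "t test will be used to compare these continuous parameters between baseline and day 15 of follow-up". The sentence follows the pooled descriptive statistics, so I read it as pooled over arms.
- Between arms: an unpaired t test, with P < 0.05 called significant. The text dates this test to day 22, while the only follow-up blood draw is on day 15. The two must be reconciled; I take day 15 here.

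No covariate, stratification, exclusion of inflamed samples or log transform is stated. The only adjustment is Benjamini-Hochberg for related hypotheses. Regression and mixed models are planned only for volume consumed.

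Two further passages matter. Section C.vii excludes a child who "Has any sign of acute illness, including but not limited to fever, cough, and diarrhea". Section D.i (Risk Considerations) expects frequent diarrhea and respiratory infection during the study, in either arm.

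**The concern.** The plan treats inflammation and micronutrient status as separate outcomes. Ferritin is the usual iron marker in such a panel, and RBP4 the vitamin A marker. As general physiology, which the documents do not discuss, ferritin rises and RBP4 falls with inflammation whatever the nutrient stores. A raw mean then mixes the two.

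The paired comparison has no control group, and its two time points are not alike. Baseline blood comes from children selected for having no acute illness. I found no such condition on the day 15 sample, and illness in between is expected. Inflammation may therefore rise between the draws whether or not AA-ORS has any effect, and the raw test would report that as a change in ferritin or RBP4.

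At stake are the reading of the exploratory objective and the quality of the setting-specific biomarker data that Section C.ii wants for planning a later efficacy trial.

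**Working it through.** **The plan's own biomarker figure.** Section C.iii (Sampling Strategy) states about 80% power for a difference of 376 ng/ml in sCD14, SD 520, 30 per arm. The noncentrality is 376 / (520 × √(2/30)) = 2.80. Power is 0.800 by the normal approximation and 0.786 by the noncentral t with 58 df. The figure reproduces and is not in dispute. No power figure is given for ferritin or RBP4.

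**Inputs from the plan.** 33 per arm with up to 10% dropout leaves 33 × 0.9 = 29.7, about 30 per arm or 60 pairs. Significance is at P < 0.05, taken as two-sided.

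**Inputs assumed, because the documents give none.**
- r, correlation of the marker with an inflammation index: 0.2 to 0.6
- s, shift of that index: 0.5 SD
- ρ, correlation of baseline with day 15 values: 0.5
- for the between-arm test: elasticity of ferritin on CRP 0.1 to 0.3, log-SD of ferritin 0.8, CRP halved by AA-ORS

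True nutrient status is held constant throughout.

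**Paired test, 60 pairs.** The marker shifts by r × s SD. The SD of a within-child difference is √(2(1 − ρ)) = 1. The noncentrality is r × s × √60, with 59 df.

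| r | marker shift (SD) | noncentrality | P < 0.05 |
|---|---|---|---|
| 0.2 | 0.10 | 0.77 | 12% |
| 0.4 | 0.20 | 1.55 | 33% |
| 0.6 | 0.30 | 2.32 | 63% |

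If the test were run within one arm (30 pairs, 29 df), r × s × √30 gives noncentralities of 0.55, 1.10 and 1.64, and rates of about 8%, 19% and 36%. Over s from 0.25 to 0.75 and ρ from 0.3 to 0.7, with 60 pairs, the range is 6% to 99%. The result depends heavily on the assumptions.

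**Between-arm test, 30 per arm.** If AA-ORS leaves inflammation alone, randomization keeps the rate at 5%. If AA-ORS halves CRP, the ferritin ratio between arms is 2^0.1 = 1.07 to 2^0.3 = 1.23. Simulated t tests on raw values, which is what the plan describes, give P < 0.05 in about 5% to 14% of trials. These rates are before Benjamini-Hochberg.

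**After adjustment.** Simulations with the inflammation index as a covariate (s = 0.5, r = 0.2, 0.4 and 0.6, paired and unpaired) return rejection to 5.0% to 5.7%. This is a best case: the index is observed without error and the model is correct.

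**The case against.** **Every driver is assumed.** The documents give no elasticity, CRP effect or marker correlation, and do not link ferritin or RBP4 to inflammation. This stands. The omission does not depend on any one value, but its size does.

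**Multiplicity is already corrected.** Benjamini-Hochberg would lower these rates. For the between-arm test with CRP halved and all other markers null, they fall to about 2% to 6% in a family of three tests and 0.3% to 2% in a family of thirteen. The plan does not state the family size, and the rates would be higher if other markers also moved. The step reduces how often the misreading is declared significant. It does not remove the bias from the means.

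**The endpoint is exploratory and declared underpowered.** True, and the limitations section promises restraint in the conclusions. None of those caveats concerns inflammation, and low power does not excuse a biased mean.

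**Adjustment can mislead too.** CRP and AGP at day 15 are measured after randomization. If AA-ORS improves nutrient status by way of inflammation, adjusting for them removes part of a real effect. This stands and shapes the fix.

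**Stronger readings the documents do not support.** A reader might infer that the arm comparison is biased as planned. That holds only if AA-ORS changes inflammation, and the support in the abstract for such an effect is from mice. A reader might also infer that baseline ferritin is badly overstated. Enrollment excludes acute illness, recent illness that might affect nutrition and household diarrhea, so subclinical inflammation is possible but its extent is unknown. Finally, since clinic-recruited children enroll "1–3 weeks after the immunization or Vit. A supplementation visit", a reader might infer that recent vitamin A distorts RBP4. Supplementation at 12 and 18 months is routine care in this setting and should be balanced by randomization, and the documents give no basis for a size.

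**Conclusion.** The concern holds as an omission in an exploratory analysis. Ferritin and RBP4 are to be compared as raw averages, with no account taken of the inflammation markers from the same assay. The before-after test is the main exposure, and a misleading result there does not require any effect of AA-ORS. The between-arm test is a lesser and conditional exposure. All rates are illustrations that rest on the assumed marker-inflammation link and on the size of the inflammation shift; they are not predictions for this trial. Safety, volume and acceptability conclusions are untouched.

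**What to change.** In Section C.xi, exploratory analysis, add inflammation-adjusted ferritin and RBP4 beside the raw values:

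1. Estimate the slopes of log ferritin and log RBP4 on log CRP and log AGP from the pooled baseline data, which treatment cannot have affected.
2. Use these slopes to adjust each child's values at both visits to one fixed low-inflammation reference.
3. Report raw and adjusted results side by side for the baseline and day 15 descriptive statistics, the paired test and the between-arm comparison.
4. Keep the raw between-arm comparison as the total effect. Label the adjusted one as the difference not explained by inflammation.

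The cost is analysis wording and a short extra analysis of data already planned, with no new assay, sample or visit. The drawbacks should be stated in the plan: slopes from about 66 children are imprecise, and adjusting for CRP and AGP measured after randomization can remove part of a real effect.

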**Study population:**

This study will recruit subjects from a health facility in Western Kenya. The study population is children 12–24 months of age with mild to moderate stunting ( $-3 < \text{LAZ} < -1$ ), who are presenting to health facilities for routine immunizations, healthy child visits, or vitamin A supplementation. Caregivers of enrolled children will also be consented for interviews and direct observation.

**Sample size:**

N = 132 total individuals

AA-ORS: 33 children; 1 dose of up to 237 ml × 14 days

Placebo solution: 33 children; 1 dose of up to 237 ml × 14 days

	Study Arm	
	AA-ORS	Placebo solution
Children	33; receive 1 dose of up to 237 ml x 14 days	33; receive 1 dose of up to 237 ml x 14 days
Caregivers	33; interviews and direct observation	33; interviews and direct observation

**Study duration:**

4 months

## A. RESEARCH STUDY PERSONNEL

**Statement of compliance:** The trial will be conducted in accordance with the International Council on Harmonisation (ICH) Good Clinical Practices (GCP) E6(R2), the Declaration of Helsinki, and applicable local regulatory requirements. The principal investigator (PI) and site PI will assure that no deviation from or changes to the protocol will take place without prior agreement from the sponsor and documented approval from the relevant ethics committees (ECs) and regulatory body, except where necessary to eliminate an immediate hazard(s) to the trial participants. All personnel involved in the conduct of this study have completed Human Subjects Protection Training.

**B. ABSTRACT**

Environmental enteric dysfunction (EED) is an intestinal disorder common among people living in low-resource settings (LRS), which in children has been associated with increased risk of growth stunting, reduced cognitive development, and reduced oral vaccine responsiveness. An effective EED therapeutic would offer an opportunity to improve child growth and development in LRS. One promising intervention, enterade® (an amino acid–based oral rehydration solution [AA-ORS]), is a medical food product already sold in the United States. It consists of oral rehydration salts and a proprietary blend of amino acids designed to restore gut function, improve nutrient and electrolyte absorption, and improve barrier integrity. There is evidence that this AA-ORS reduces inflammation and promotes healing of damaged intestinal epithelium in murine models of intestinal damage (irradiated gut), and it may provide benefit to pediatric EED patients. Supplementation of amino acids may lessen or improve intestinal injury related to enteric illnesses commonly experienced in settings of poor hygiene and sanitation infrastructure. We will conduct a randomized, double-blinded, placebo-controlled pilot study in Kakamega County, Kenya, to assess the safety, feasible dosage, and acceptability/tolerability of the product in the target population (children aged 12–24 months) and their caregivers.

